### 3.2 Rationale for the research project

Based on the background described above, the rationale for this study can be summarized as followed.

1) Many critically ill children and neonates need intensive care therapy to maintain adequate blood flow and arterial blood pressure. 2) The side effects of abundant fluid administration and catecholamine therapy may be harmful for patients in critical care. An additional fluid and catecholamine sparing therapy is desirable. 3) Some patients with persistent vascular hypotension show low endogenous vasopressin levels. 4) These patients have to be identified to administer exogenous vasopressin. 5) Identification of these patients can only be achieved via determination of the stable vasopressin-by-product copeptin rather than via direct laboratory assessment of the instable endogenous vasopressin.

Accurate identification of patients with persistent low vasopressin/copeptin levels would facilitate future individual vasopressin therapy to support and replace, at least in part, catecholamines and fluids in severe arterial hypotension and shock.

As numbers studied for the correlation of copeptin and arterial hypotension in paediatric and neonatal critical care settings are small, this prospective observational study has to be performed.

The actual effect of exogenous vasopressin therapy in patients with low blood copeptin levels will have to be tested in a follow-up interventional trial.

### **3.3 Risk-Benefit Assessment**

The study period will cover up to 168 hours in which a maximum of 6 blood samples (minimum 600 µl each) from peripheral venous lines or central venous and arterial catheters will be analysed for baseline copeptin distribution. The required amounts of blood volume for analyses are clinically not relevant for any age group. As critically ill patients frequently require invasive arterial blood pressure monitoring and central venous access for fluid and medicament administration, the required catheters for blood withdrawal are generally in place. Importantly, each study blood withdrawal will be grouped together with otherwise medically indicated blood withdrawals, causing no additional catheter manipulation, pain or harm for the patient. The comparison of blood copeptin and arterial hypotension will define the primary endpoint.

All further laboratory parameters proposed in “Schedule of Assessments (Flow of Research Project)” are considered to be secondary endpoints. Analyses of these laboratory values will only be included in the study, if their sampling is indicated for any other medical reason.

Children and neonates included in this study do not directly benefit from the study. However, the recruited patients help to identify future patient cohorts, which could benefit from individualized vasopressin administration supporting and replacing at least a part of the current standard fluid and catecholamine therapy in hypotension and shock. Moreover, the potential association between copeptin levels and outcome might provide new insights when it comes to counselling parents experiencing an emotionally challenging period of their lives.

Security of the collected data is given through data collection in especially signed folders (including case report forms) in the intensive care ward and through data storage in an especially signed electronic file (University Children’s Hospital Zurich). Data in the folders on the ward contain only data stored in clinical patient files anyway. Data will be managed strictly confidential, after initial data acquisition data will be coded through electronic storage with a study number and age (years + months, if <28 d in days); access to original data will only be given to the study personal and to institutions mentioned above. There will be no transfer of non-coded data to other storage systems outside the University Children’s Hospital Zurich.

## **4. OBJECTIVES, ENPOINTS/OUTCOMES AND OTHER STUDY VARIABLES**

### **4.1 Objectives**

#### **Primary objective**

The primary objective is to investigate the average change of blood copeptin levels in critically ill children and neonates with both arterial normo- and hypotension over 48h after intensive care unit (ICU) admission, and in a second step to describe the natural course and variability of copeptin levels over a period of up to 7 days after ICU admission. In this scope we will also investigate the association of patient characteristics (covariates) with blood copeptin baseline levels at ICU admission and the course of blood copeptin levels during ICU stay. In particular the association with the following factors will be investigated:

- Arterial blood pressure (in particular hypotension vs. normotension), to identify patients that may most benefit from exogenous AVP treatment
- Septic shock
- Heart failure
- Traumatic head injury, brain tumor and/or intracranial operation
- Perinatal asphyxia
- Severity of disease (disease score)
- Age

#### **Secondary objective**

The secondary objective is to explore the association of individual copeptin levels over up to 7 days with the following clinical outcomes:

- a. Length of stay on the intensive care unit
- b. Length of respiratory support
- c. Length and dose of catecholamine therapy (as a marker of severity of disease and degree of arterial hypotension)
- d. Rate of death at day 28,

and to explore the temporal and dynamic relationship between the course of blood pressure, blood copeptin levels and catecholamine therapy over time.

## 4.2 Primary and secondary endpoint/outcome(s)

The primary endpoint of this study is descriptive, since the primary objective is simply to better understand which paediatric patients admitted to the ICU are likely to present with arterial hypotension in the presence of low copeptin levels over an observation period of up to 7 days. Results are expected to allow defining a group of patients that may benefit the most from exogenous AVP therapy. The effectiveness of exogenous AVP administration to patients with low AVP would have to be tested in a follow-up interventional trial. The patients participating in this present observational study will not receive any study medicaments.

### Definition and measurement of variables relevant to primary endpoint:

#### Copeptin levels

Blood copeptin values measured by the B·R·A·H·M·S Copeptin KRYPTOR (Thermo Fisher Scientific, Hennigsdorf, Germany) in all critical ill children and neonates admitted to the intensive care unit (ICU) will be analysed. Time points for blood sampling will be at ICU admission and then determined by other medical indications but scheduled to be performed with approximately 12, 24, and 48. Time points for all patients staying longer than 48 hours will be 96 and 168 hours to capture the presumed copeptin pattern in children. For the endogenous active hormone AVP it could be shown by Lee et al. in 2013 that AVP stays elevated for 120 hours/5 days after onset of shock, but actual duration of AVP/copeptin elevation is unknown in children. Therefore, a last measurement with seven days will be included to show a potential decline of copeptin after the resolution of shock.

#### Arterial blood pressure and hypotension

Hypotension is defined as systolic arterial pressure below age specific 5th percentiles according to reference values established in the context of the last International Pediatric Sepsis Consensus Conference (published 2005): newborn 0 days to 1 week 59 mmHg, neonate 1 week to 1 month 79 mmHg, infant 1 month to 1 year 75 mmHg, toddlers and preschool children 1 to 5 years 74 mmHg, school age children 5 to 12 years 83 mmHg, adolescent and young adult 12 to 18 years 90 mmHg. Blood pressure will be measured invasively via indwelling central or peripheral arterial catheters or non-invasively via auscultatory or oscillometric techniques.

#### Septic shock

For the definition of “septic shock” sepsis, systemic inflammatory reaction (SIRS), and septic shock have to be defined.

Sepsis will be defined as systemic inflammatory reaction (SIRS) in the presence of suspected or proven infection. SIRS will be defined as the presence of at least two of the following four criteria, one of which must be abnormal temperature or leukocyte count: 1) Core temperature of >38.5°C or <36°C. 2) Tachycardia, defined as a mean heart rate >2 SD above normal for age in the absence of external stimulus, chronic drugs, or painful stimuli; or otherwise unexplained persistent elevation over a 0.5- to 4-hr time period OR for children <1 year old: bradycardia, defined as a mean heart rate <5th percentile for age in the absence of external vagal stimulus, beta-blocking drugs, or congenital heart disease; or otherwise unexplained persistent depression over a 0.5-hr time period. 3) Mean respiratory rate >2 SD above normal for age or mechanical ventilation for an acute process not related to underlying neuromuscular disease or the receipt of general anaesthesia. 4) Leukocyte count elevated or depressed for age (not secondary to chemotherapy-induced leukopenia) or >10% immature neutrophils. For all reference values see Table 1).

TABLE 1

Age Group	Heart Rate Tachycardia Beats/min	Heart Rate Bradycardia Beats/min	Respiratory Rate Breaths/Min	Leukocyte Count 10  /mm 	Systolic Blood Pressure mmHG
0 days to 1 wk.	>180	<100	<50	>34	<59
1 wk. to 1 mo.	>180	<100	<40	>19.5 or <5	<79
1 mo. to 1 yr.	>180	<90	<34	>17.5 or <5	<75
2-5 yrs.	>140	NA	<22	>15.5 or <6	<74
6-12 yrs.	>130	NA	<18	>13.5 or <4.5	<83
13 to <18 yrs.	>110	NA	<14	>11 or <4.5	<90

Age-specific vital signs and laboratory variables (5th percentile for lower values for heart rate, leukocyte count, and systolic blood pressure and 95th percentile for upper values for heart rate, respiration rate, or leukocyte count)

Infection may be suspected or proven. Infection may be suspected by a clinical syndrome associated with a high probability of infection. Evidence of infection includes positive findings on clinical exam, imaging, or laboratory

tests (e.g. white blood cells in a normally sterile body fluid, perforated viscus, and chest radiograph consistent with pneumonia, petechial or purpuric rash, or purpura fulminans). Infection will be defined as proven by positive culture, tissue stain, or polymerase chain reaction test and may be caused by any pathogen.

Septic shock is defined as sepsis AND cardiovascular organ dysfunction (“Organ dysfunction criteria”, section on cardiovascular dysfunction later this chapter).

### **Heart failure**

All patients with structural or functional impairment of heart function, leading to an inadequate amount of blood being pumped through the body, will be analysed as subgroup. Type of cardiopathy, cardiac lesions, preoperative medication, echocardiographic and cardiac catheter results, periods of cardiopulmonary bypass, cross clamping, deep hypothermic arrest, modified ultrafiltration, anaesthetics used, type of surgery, and the postoperative echocardiographic and laboratory results will be recorded for each patient. Patients will be defined as having preoperative congestive heart failure if they are treated with digoxin, diuretics, inhibitors of angiotensin converting enzyme, beta-blockers, or milrinone, or if they have congestive cardiac failure listed as diagnosis.

### **Traumatic head injury, brain tumour and brain operation**

All children and adolescents with traumatic head injury, brain tumour and/or brain operation will be analysed as subgroup. Glasgow coma scale on admission and post resuscitation, presence and history of seizures, CT abnormalities as abnormal cisterns, midline shift  $>5$  mm, traumatic subarachnoidal haemorrhage, performance and type of intracranial surgery will be noted for each patient. In addition, intracranial pressure values and cerebral perfusion pressures will be recorded at each visit.

### **Perinatal asphyxia**

Perinatal asphyxia causes neonatal encephalopathy. This is a clinically defined syndrome of disturbed neurologic function in the earliest days of life in an infant born at or beyond 35 weeks of gestation, manifested by a subnormal level of consciousness or seizures, and often accompanied by difficulty with initiating and maintaining respiration and depression of tone and reflexes. To assess children with neonatal asphyxia and consecutive encephalopathy, the following neonatal signs consistent with an acute peripartum or intrapartum hypoxic event must be met for study subgroup inclusion: Gestational age  $\geq 35$  weeks AND an Apgar score of  $<5$  at 5 minutes and 10 minutes AND a foetal umbilical artery acidaemia: foetal umbilical artery pH  $<7.15$ , and/or base deficit  $\geq 12$  mmol/L AND presence of multisystem organ failure consistent with hypoxic-ischemic encephalopathy (two or more dysfunctional organ systems mentioned in section “Organ dysfunction criteria”). One important point defining hypoxic-ischemic encephalopathy is neuroimaging evidence of acute brain injury seen on brain magnet resonance imaging (MRI) consistent with hypoxia-ischemia (i.e. deep nuclear grey matter (basal ganglia or thalamus) and/or watershed cortical injury). As this imaging is usually performed after 96 hours of patient cooling in moderate and severe cases, it cannot be mandatory for study inclusion, but if available will be part of endpoint analysis.

For endpoint assessment, the following will be noted: gestational age, Apgar-score, arterial umbilical cord pH, blood gas analysis, lactate, presence of arterial hypotension as defined as mean arterial pressure below the gestational age limit treated with intravenous corticosteroids, fluids and/or catecholamines, results of neurological imaging (cranial ultrasound and/or MRI), and performance of neonatal cooling as prevention of neurological damage.

### **Organ dysfunction criteria:**

#### **Cardiovascular dysfunction**

Despite administration of isotonic intravenous fluid bolus  $\geq 40$  mL/kg in 1 hr:

- Decrease in BP (hypotension)  $<5$ th percentile for age or systolic BP  $<2$  SD below normal for age

OR

- Need for vasoactive drug to maintain BP in normal range (dopamine, dobutamine, epinephrine, norepinephrine or vasopressin at any dose)

OR

- Two of the following:

Unexplained metabolic acidosis: base deficit  $>5.0$  mmol/L

Increased arterial lactate  $>2$  times upper limit of normal (2.0 mmol/L)

Oliguria: urine output  $<0.5$  mL/kg/hr

Prolonged capillary refill:  $>5$  s

Core to peripheral temperature gap  $>3^{\circ}\text{C}$

#### **Respiratory dysfunction**

- $\text{PaO}_2/\text{FIO}_2 <40$  kPa in absence of cyanotic heart disease or pre-existing lung disease (i.e. acute respiratory distress syndrome (ARDS)) and acute lung injury (ALI). ARDS must include a  $\text{PaO}_2/\text{FIO}_2$  ratio  $\leq 26.6$  kPa,

bilateral infiltrates, acute onset, and no evidence of left heart failure. ALI is defined identically except the PaO2/FIO2 ratio must be  $\leq 40$  kPa.

OR

- PaCO2  $> 2.6$  kPa over baseline PaCO2

OR

- Proven need (assumes oxygen requirement was tested by decreasing flow with subsequent increase in flow if required) or  $> 50\%$  FIO2 to maintain saturation  $\geq 92\%$

OR

- Need for nonselective invasive or non-invasive mechanical ventilation (postoperatively, this requirement can be met if the patient has developed an acute inflammatory or infectious process in the lungs that prevents him or her from being extubated)

#### Neurologic dysfunction

- Glasgow Coma Score  $\leq 11$

OR

- Acute change in mental status with a decrease in Glasgow Coma Score  $\geq 3$  points from abnormal baseline

#### Hematologic dysfunction

- Platelet count  $< 80,000/\text{mm}^3$  or a decline of 50% in platelet count from highest value recorded over the past 3 days (for chronic haematology/oncology patients)

OR

- International normalized ratio  $> 2$

#### Renal dysfunction

- Serum creatinine  $\geq 2$  times upper limit of normal for age or 2-fold increase in baseline creatinine
- Reference values: newborn 27 to 88  $\mu\text{mol/L}$ ; infant 18 to 35  $\mu\text{mol/L}$ ; child 27 to 62  $\mu\text{mol/L}$ ; adolescent 44 to 88  $\mu\text{mol/L}$ 

#### Hepatic dysfunction

- Total bilirubin  $\geq 4$  mg/dL (not applicable for newborn)

OR

- Alanine transaminase (ALT) 2 times upper limit of normal for age
- Reference values (95th percentile): newborn – 18 month male: 60 U/L, female 55 U/L; 18 month – 5 years male 40 U/L, female 35 U/L; 5 – 8 years male 35 U/L, female 35; 9 – 13 years 44 U/L, female 35 U/L; 13 – 18 years male 69 U/L; female 35 U/L

#### Severity of disease:

Only one of the following disease scores will be evaluated per patient as appropriate for the respective age group

- Paediatric Index of Mortality 2 (PIM 2): results in “predicted mortality risk” (range: 0-100%), calculated from available patient data at admission
- Simplified Acute Physiology Score (SAPS II): results in an integer point score between 0 and 163 and a predicted mortality between 0% and 100%, calculated from 12 routine physiological measurements collected during first 24h after ICU admission (age, heart rate, systolic blood pressure)
- Clinical Risk Index for Babies (CRIB II) : results in a score ranging from 0 to 27 and mortality probability ranging from 0-100%, calculated at admission from five variables (sex, birth weight, gestational age, temperature, base excess).

#### Age:

- Patients` age will be noted on study entrance.

#### **Definition and measurement of variables relevant to secondary endpoints:**

a) Length of ICU stay will be noted in hours.

b) Length of respiratory support will be noted in hours, stratified by invasive and non-invasive ventilatory support.

c) Length of catecholamine therapy will be noted in hours separately for every drug. In addition, the inotropic score for the estimation of amount of vasopressors used will be calculated with the equation by Wernovsky modified by Choong et al.: 1 point will be given for every  $\mu\text{g}/\text{kg}/\text{min}$  dopamine or dobutamine, 10 points will be given for every  $\mu\text{g}/\text{kg}/\text{min}$  milrinone and 100 points will be given for every  $\mu\text{g}/\text{kg}/\text{min}$  adrenaline or noradrenaline.

e) Death will be noted, rate of death at 28 days will be correlated with blood copeptin level.

Copeptin in critically ill Paediatric and Neonatal Intensive Care patients and its association with arterial hypotension – The COPNIC-Study

Version 2.2 (17/08/2017)

page 17 of 27

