# **3. INTRODUCTION**

## **3.1 Background**

The aim of this prospective observational study is to characterize the course and progression of the biomarker copeptin in critically ill neonates and children. Copeptin values have the potential to be associated with outcome and to serve as a therapeutic guide for exogenous vasopressin administration in severe arterial hypotension and shock.

Paediatric intensive care patients very often suffer severe arterial hypotension in various clinical situations with cardiac and respiratory failure, e.g. septic shock, asphyxia, brain injury, and after several types of operations. Septic shock is associated with a very high mortality up to 50% mainly due to an excessive rate of hypoperfusion-related multiorgan dysfunction (up to 80% in severe sepsis or septic shock). Treatment for shock in general includes fluid and catecholamine administration to maintain adequate blood flow and sufficient oxygen transport to peripheral tissues. Fluid resuscitation may lead to volume overload and pulmonary edema bearing additional risks. In addition, large volumes of fluids administered over a short period of time may lead to heart failure. Though catecholamines deliver strong fluid sparing arterial pressure support, they can place the patient with instable cardiovascular state at risk for severe complications (i.e. arrhythmia, right and left ventricular after load augmentation, reduced tissue blood flow).

In recent years, several authors have reported the use of intravenous vasopressin in addition to or instead of standard antihypotensive treatment. Vasopressin is not a catecholamine but a natural endogenous hormone with less toxic side effects. It may help to reduce fluid and catecholamine use. Its main endogenous function is maintenance of water- and electrolyte balance, as renal V2-Arginine-Vasopressin (AVP) receptors in the collecting duct mediate water reabsorption via induction of intracellular cAMP (Cyclic adenosine monophosphate) production and reversible translocation of the water channel "aquaporin 2" from cytoplasmic vesicles to the apical cell membrane. But in addition, it has strong dose-dependent vasoconstrictive effects on the peripheral vessels mediated via the V1-vascular AVP-receptor.

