### 4.3 Other study variables

The following endpoints will be noted, as copeptin results may differ when stratified according to:

- Weight
- Sex
- Postnatal days and postconceptional age in neonates
- Exogenous vasopressin administration

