#### **Secondary endpoints**

Finally, measured blood copeptin levels and/or model-derived individual parameters characterizing the course of individual blood copeptin levels will be investigated as predictor variables for length of ICU stay, length of respiratory support and survival in a time-to-event analysis, and for severity of disease (including dose of catecholamine therapy) in a regression analysis.

In a more advanced analysis, also the time-course of blood pressure measurements will be analysed and characterized in a mixed-effect regression analysis. The temporal and dynamic relationship between blood copeptin and blood pressure will be furthermore assessed.

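### The inotropic score used for catecholamine dose leaves out vasopressin and counts milrinone, so it measures neither catecholamine dose nor total pressor support

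*Protocol*

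**What the plan says.** Protocol section 4.2, item c) of the variables relevant to secondary endpoints, states that "the inotropic score for the estimation of amount of vasopressors used will be calculated" from a cited equation. For dopamine or dobutamine, "1 point will be given for every" µg/kg/min; for milrinone, "10 points will be given for every" µg/kg/min; adrenaline and noradrenaline earn 100 points per µg/kg/min. Vasopressin does not appear in the equation.

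The endpoint that the score serves is named in section 4.1, secondary objective: "Length and dose of catecholamine therapy (as a marker of severity of disease and degree of arterial hypotension". Section 8.2.1, secondary endpoints, then uses copeptin as a predictor "for severity of disease (including dose of catecholamine therapy) in a regression analysis".

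Elsewhere the protocol treats vasopressin as follows:

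- Section 4.2, cardiovascular dysfunction, includes it in the drug criterion: "Need for vasoactive drug to maintain BP in normal range (dopamine, dobutamine, epinephrine, norepinephrine or vasopressin at any dose". Milrinone is not in that list.
- Section 3.1 states that vasopressin is not a catecholamine and says of it: "It may help to reduce fluid and catecholamine use".
- Section 4.3 lists "Exogenous vasopressin administration" as a variable by which copeptin results may differ. Section 7.4 records it on the case report form together with other drugs.

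Milrinone appears in section 4.2, heart failure, as one of the treatments that define preoperative congestive heart failure.

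**The concern.** The protocol gives one number three descriptions: amount of vasopressors, dose of catecholamine therapy, and marker of severity and degree of hypotension. The equation fits none of them fully. As a measure of pressor support it lacks a drug that the protocol itself counts as such. As a measure of catecholamine dose it contains milrinone.

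Vasopressin is central to this study. The aim is to find hypotensive children with low copeptin who might benefit from it, and some enrolled children may receive it clinically, since the protocol records its use. If vasopressin replaces part of a child's catecholamine in such a case, the score falls and section 8.2.1 would treat that as lower severity. The same problem reaches the planned analysis of how blood pressure, copeptin and catecholamine therapy move together, because infused vasopressin may act on pressure without showing in the score.

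**Working it through.** The protocol states no figure for this point, so there is none to reproduce. The check is to evaluate the equation as written.

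**Formula** (section 4.2, item c; all doses in µg/kg/min):

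score = 1 × (dopamine + dobutamine) + 10 × milrinone + 100 × (adrenaline + noradrenaline)

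Vasopressin has no term, so its implied weight is 0.

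**Assumed doses.** The protocol gives no doses. Those below are chosen only to show the arithmetic and say nothing about treatment.

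*Vasopressin replacing noradrenaline*

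| Noradrenaline before | Score before | Half replaced by vasopressin | Fully replaced |
|---|---|---|---|
| 0.05 | 100 × 0.05 = 5 | 2.5 | 0 |
| 0.1 | 100 × 0.1 = 10 | 5 | 0 |
| 0.3 | 100 × 0.3 = 30 | 15 | 0 |
| 0.5 | 100 × 0.5 = 50 | 25 | 0 |

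A partial reduction from 0.3 to 0.1 while vasopressin is added takes the score from 30 to 10, a fall of (30 − 10)/30 = 67%.

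*Milrinone*

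- Milrinone 0.5 alone: 10 × 0.5 = 5, equal to dopamine 5 alone (1 × 5 = 5).
- Milrinone 0.5 with noradrenaline 0.1: 5 + 10 = 15. If vasopressin replaces the noradrenaline: 5 + 0 = 5.

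**Set against the protocol's own definitions**

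| Child receives | Drug criterion, cardiovascular dysfunction (fluid condition met) | Score |
|---|---|---|
| No vasoactive drug | not met | 0 |
| Vasopressin alone, to maintain pressure | met, at any dose | 0 |
| Milrinone 0.5 alone | milrinone not listed | 5 |

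The score ranks the third child above the second and cannot tell the second from the first. The drug criterion orders them differently.

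**What a catecholamine-only version would change.** Without the milrinone term, the third child scores 0, and milrinone 0.5 with noradrenaline 0.1 scores 10. The child on vasopressin alone still scores 0. Removing milrinone therefore makes the score match its name but does not close the vasopressin gap. Only using the exposure information in the analysis does that.

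**What cannot be calculated.** The effect on the copeptin-severity association depends on the share of children given vasopressin, on how far their catecholamines are reduced, and on how both relate to copeptin. The protocol gives none of these.

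**The case against.** The best defence is that the endpoint is called catecholamine dose, that section 3.1 says vasopressin is not a catecholamine, and that its absence is therefore correct. The cardiovascular dysfunction list has another job, a yes/no classification, and need not match. On this view the only slip is the word vasopressors in section 4.2. This is partly right, but it does not explain why milrinone is scored, and it leaves untouched the reading in section 4.1 as degree of hypotension, which a catecholamine-only number cannot carry for children on vasopressin. That milrinone is not a catecholamine is general pharmacology and is not stated in the protocol; the protocol's own lists show only that it is handled as a heart-failure treatment and is absent from the pressor criterion.

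Several other objections stand:

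- A reader might infer that the score necessarily falls when vasopressin is started, so that a switched child always appears to improve. Section 3.1 says only that vasopressin may help to reduce catecholamine use, and section 3.1 also notes that not all treated children had an adequate rise in pressure. A fall is possible, not certain.
- A reader might also infer that the low-copeptin/severity association is biased towards or past zero. No figure in the protocol supports a direction.
- Vasopressin use is already recorded and recognised as relevant to copeptin results. Length of therapy is noted for each drug, and severity is also captured by PIM 2, SAPS II or CRIB II. However, section 4.3 ties the stratification to copeptin results, not to the score or to the dose regression.
- Choice of model covariates is commonly left to an SAP, and none was available here. Their absence is not the defect. The defect is that the protocol fixes an equation, a purpose and a reading that do not agree, which an SAP following it would inherit.
- The score is a cited instrument, so replacing it outright would lose comparability.

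**Conclusion.** The mismatch is real and follows from the protocol's text: the score measures neither catecholamine dose nor total pressor support. It can understate support in children given vasopressin, down to 0 for a child on vasopressin alone, and it scores children on milrinone alone as if they received catecholamines.

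The consequence is limited. It concerns one secondary, exploratory endpoint and the related dynamic analysis in an observational study. The primary endpoint and the sample size of 170 are untouched. The size and direction of bias are unknown, and if few children receive vasopressin the effect will be small. The numerical examples rest on assumed doses. This is a worthwhile low-cost improvement, not a threat to the study's main result.

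**What to change.** 1. In section 4.2, item c), state that the score does not capture vasopressin, and reconcile the wording with section 4.1 on whether the endpoint is catecholamine dose or total vasoactive support.
2. Keep the cited score for comparability. Alongside it, report a catecholamine-only score, 1 × (dopamine + dobutamine) + 100 × (adrenaline + noradrenaline), and show milrinone separately.
3. In section 8.2.1 (or an SAP that implements it), include the recorded exogenous vasopressin exposure as a time-varying term or a stratum in the dose regression and in the blood pressure-copeptin-catecholamine analysis, so that exposed children are not read as unsupported. Report how many children were exposed.
4. Treat any analysis that leaves out exposed intervals as a sensitivity analysis only, and state its risk: vasopressin may be given because of hypotension, so leaving out exposed intervals can select against the children of most interest.

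Cost: a few lines of text, one extra version of the score and one extra model term. Exposure is already collected and treatment is unaffected. If few children are exposed, the added term will be estimated with little precision.
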